5.1 Inclusion Criteria

In order to participate in this study, volunteers must satisfy all of the following criteria:

- Aged >65 years
- Have attended the Memory Clinic at the RICE Centre in Bath
- Mini-mental state examination (MMSE) score of ≥ 20 [21]
- Short Physical Performance Battery (SPPB) [22] score 3-8 and not scoring 0 on any component of the test
- Capability to safely perform the exercise snacking movements, assessed by a researcher during screening, and be able to have someone present in the home who could call for help if required during all exercise snacks.
- Not regularly engaging in recreational sports or structured exercise (once a week or more).
- Have a foreseeable clear period of 28 consecutive days in which to perform the exercise snacking protocol (i.e. no planned holidays or hospitalisation)

5.2 Exclusion Criteria

Participants will not be able to take part in this study if they meet any one of the following criteria:

- Co-morbidity preventing participation (e.g. severe breathlessness, pain, psychosis, Parkinson's, Dementia with Lewy Bodies, or other severe neurological disease)
- Individuals with a history of bone, joint or neuromuscular problems or a current musculoskeletal injury ascertained through preliminary screening that would prevent exercise snacking or be made worse by performing exercise snacking.
- Individuals with contraindications to exercise including chest pain, dizziness, or loss of consciousness, or who have been instructed by their doctor to only do physical activity recommended by them.

6. Possible Risks/Discomforts

The study involves participation in small bouts of exercise that the participants may find demanding. However, feelings of tiredness associated with the exercise are transient and will pass quickly. The researchers will be at all times vigilant in their observations of participants performing under the prescribed exercise conditions and are ready to end any testing session should the participant report, or even appear to be unduly stressed. The physical function tests are specifically designed to mimic ambulatory activities of daily living and are therefore movement patterns that the participants will be used to completing and will not find challenging.

Undertaking exercise in the home poses a risk of falling in this population, and as such participants should not perform the exercise snacks alone in the home and should at all times during exercise snacking bouts be in the presence of a carer or member of the household with functional capacity to request immediate assistance. Moreover, whilst participants are encouraged to complete as many repetitions of each exercise as possible in a minute, emphasis is placed on those repetitions being completed safely and in a controlled manner. This is to ensure that balance and movement control throughout the range of movement is mildly challenged so as to stimulate improvement, but within the remit of simple, everyday movements. Furthermore, should the participant feel that there is a risk of losing balance, they may hold onto a chair or stable object (doorframe) during the exercises as a precautionary measure. The exercise bouts are deliberately very brief with structured rest intervals, and should not cause muscle soreness or compromised function after a bout.

All of the above will be explained to the potential participant verbally and in the participant information sheet to ensure that they are fully informed before giving consent. The exercise snacking logbook will have emergency contact numbers for participants should the need arise.

7. Recruitment and Screening

Potentially eligible patients will be identified by RICE gerontologists, based on their clinical judgement. Written information about the study will be provided to the potential participant, and they will be asked to provide consent to be contacted by a member of the study team. During an initial phone contact with a potential participant, a member of the study team will provide a verbal overview of the study, and ask if the participant believes they meet all of the inclusion criteria and none of the exclusion criteria based on the written information provided. If this is the case, potential participants will be invited to arrange a screening meeting at RICE. During this meeting, potential participants will

be asked to sign an informed consent form stating their willingness to participate in the study and undergo the eligibility screening with a member of the research team. Eligible participants will be invited to take part in rest of the study, and one of the researchers will describe the study verbally to them again and provide the opportunity for potential participants to gain clarification on any aspect of the study.

8. Informed Consent

It is the responsibility of a researcher to obtain written (signed and dated by the participant and researcher) informed consent before undertaking eligibility screening and enrolling a participant in the study. This must be undertaken after adequate explanation of the aims, methods, objectives and potential hazards of the study. The researcher will also explain to the participants that they are completely free to refuse to enter the study or to withdraw from it at any time without any repercussions. Should the researcher feel that the participant does not fully understand what is being asked of them for the study, that participant will not be eligible to participate in the study. Should the participant lose capacity to consent during the study, they will be withdrawn from the study.

9. Confidentiality

A single password protected Excel data sheet maintained on a RICE computer will be used to record participant names and relevant contact information associated with a given participant ID code. This will exist for logistical purposes of running the study, and only the designated researchers will have access to this identifying information. All other non-identifying participant information and results will be stored on Excel data sheets with the participant ID code only.

For participants that opt it, an audio recording of a qualitative interview undertaken at the second visit to RICE will be taken. The information provided will be transcribed and analysed later with all identifying information removed. The audio file will be deleted once the information has been transcribed.

Any results published from this study will be anonymous and include no identifiable information.

10. References

1. Mitchell, W.K., et al., *Sarcopenia, dynapenia and the impact of advancing age on human skeletal muscle size and strength; a quantitative review*. *Frontiers in Physiology*, 2012. **3**.
2. Degens, H. and M.T. Korhonen, *Factors contributing to the variability in muscle ageing*. *Maturitas*, 2012. **73**(3): p. 197-201.
3. Seene, T. and P. Kaasik, *Muscle weakness in the elderly: role of sarcopenia, dynapenia, and possibilities for rehabilitation*. *European Review of Aging and Physical Activity*, 2012. **9**(2): p. 109-117.
4. Sousa, A.S., et al., *Financial impact of sarcopenia on hospitalization costs*. *Eur J Clin Nutr*, 2016. **70**(9): p. 1046-51.
5. Pinedo-Villanueva, R., et al., *Health Care Costs Associated With Muscle Weakness: A UK Population-Based Estimate*. *Calcified Tissue International*, 2019. **104**(2): p. 137-144.
6. Scuffham, P., S. Chaplin, and R. Legood, *Incidence and costs of unintentional falls in older people in the United Kingdom*. *Journal of Epidemiology and Community Health*, 2003. **57**(9): p. 740-744.
7. Comans, T.A., et al., *The increase in healthcare costs associated with frailty in older people discharged to a post-acute transition care program*. *Age Ageing*, 2016. **45**(2): p. 317-20.
8. Faulkner, J.A., et al., *Age-related changes in the structure and function of skeletal muscles*. *Clinical and Experimental Pharmacology and Physiology*, 2007. **34**(11): p. 1091-1096.

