4.4.2 Screening

All potential participants will undergo a face-to-face screening meeting with a member of the research team at the RICE Centre, to assess eligibility based on criteria described in Section 5 before proceeding. If the participant has a carer, then they may also attend the session. Potential participants will be asked to wear clothes in which it is comfortable to complete simple movement tasks. Before commencing any assessment, the screening and study procedures will be verbally described to the potential participant by the researcher, and they will be given the opportunity to ask questions about the study. If the potential participant is happy to continue with the screening and the study, subject to meeting eligibility criteria, they will be asked to sign an informed consent form.

A stadiometer and balance scales will be used to determine the potential participant's height and weight for calculation of Body Mass Index (BMI). Potential participants will complete a bespoke health screening questionnaire based on study exclusion criteria, and mini-mental state examination (MMSE) [21]. Those identified as meeting any exclusion criteria or with an MMSE score of <20 will be excluded from the study at that point.

Potential participants will then undertake an objective assessment of physical function (Short Physical Performance Battery; SPPB [22]) in which simple tests of walking speed, ability to repeatedly rise from a chair, and simple standing balance are scored based on set criteria. Only participants scoring over three and no more than eight out of twelve, without scoring zero on any element of the test will be eligible to continue the

screening. The upper limit to the SPPB eligibility criteria is to deliberately target a cohort who demonstrate some degree of compromised strength and balance.

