4.4.3 Baseline assessment

Baseline questionnaires and cognitive tests will be completed (paper form). The questionnaires will include brief measures of attitudes- (Outcome Expectancy for Exercise Questionnaire), self-confidence- (barrier self-efficacy scale), and psychological need satisfaction- (PNSE) for exercise, and a series of questionnaires designed to evaluate current mental health (Patient Health Questionnaire, Generalised Anxiety Disorder Assessment and Subjective Vitality Index), General Health (Short Form Health Survey) and Quality of Life (Life Satisfaction Scale, Global Quality of Life Scale). Measures of health and wellbeing will include a researcher led cognitive test (Montreal Cognitive Assessment), the Gronigen Frailty Indicator (GFI) [23].

As a collective measure of physical function, the SPPB score from the screening will be used, with the additional assessment of physical function described herein only undertaken with participants that have passed the screening and chosen to enrol in the study

Lower limb functional capacity will be assessed by a 60-second sit-to-stand test (STS-60) from a standardised, firm seated chair. For this assessment, as many sit-to-stand repetitions as possible will be completed, with the participant initially sitting fully on the chair, and rising to a full standing height with knees extended, without the use of arms for assistance with movement. Arm movement to maintain balance will be permitted, however the participant will be encouraged to minimise use of the arms to push off from the chair during the movement, rather the legs should initiate the movement. Whilst timing and counting the number repetitions performed, the researcher will be at all times vigilant to any potential loss of balance, and will stop the test if they feel the participant is unduly stressed or at risk of falling. The chair seat height will be 45 cm (the height of a standard kitchen chair). Participants will not be able to see the time remaining on the test, and no verbal encouragement will be provided. Immediately after completing the STS-60, participants will be asked to provide a rating of perceived exertion for the test using the 7-20 Borg scale [24].

As a measure of static standing balance, participants will be asked to complete simple tests of standing balance lasting a maximum of 60 seconds. Tests will consist of feet in

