semi-tandem stance, full-tandem stance, and single leg standing, with each leg tested in the single leg balance test. The aim of each test is to maintain balance for as long as possible, up to 60 seconds. Each configuration of feet position will be tested twice, with the highest score of the two taken. The first point in time at which either feet or arms are moved substantially (i.e. loss of balance has occurred) will conclude that attempt. The researcher will stand close to the participant to provide physical support if the participant appears to be losing balance, and it will be explained to the participant that they should move from the given stance being tested to prevent falling if necessary

As a measure of functional mobility, participants will be asked to complete a timed-up-and-go test (TUG), in which participants rise from a chair, walk 3 meters, turn around, walk back to the chair, and return to a seated position [25]. This test will also be completed twice, with the fastest time taken.

To assess habitual physical activity levels during the first week of the intervention, participants will then be instructed in the use of, and given a wearable physical activity monitor (ActivPAL). They will be asked to wear the ActivPAL for seven consecutive 24-hour days, and will be provided with a pre-paid and addressed envelope in which to return the device. The ActivPAL provides data on sit-to-stand transitions, and thus will also act as an intervention compliance assessment tool.

Participants will be given an exercise snacking logbook containing full written instructions on how to complete a bout of exercise snacking, and also be given verbal instruction and opportunity to ask questions on its use. The logbook includes space in which to record notes about each exercise snack that may be useful to the researcher or the participant. With the logbook for reference, the participant will perform a bout of exercise snacking as a familiarisation before leaving. The 28-day intervention period will begin the day after the screening and baseline assessment takes place.

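### Section 6 says participants will not find the function tests challenging and names no fall risk for them, which contradicts how the STS-60 and standing balance tests are run

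*Combined protocol and SAP*

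**What the plan says.** Section 6 (Possible Risks/Discomforts) says the physical function tests imitate everyday activity and "are therefore movement patterns that the participants will be used to completing and will not find challenging". The sentence covers all the tests and carries no qualification. The same section names a risk of falling for exercise in the home, but not for the tests. It closes: "All of the above will be explained to the potential participant verbally and in the participant information sheet", with the stated purpose of informing people fully before consent.

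Section 4.4.3 (Baseline assessment) sets out the tests:

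- **STS-60:** "as many sit-to-stand repetitions as possible will be completed" in 60 seconds, without the arms assisting the movement. The researcher "will stop the test if they feel the participant is unduly stressed or at risk of falling". Straight afterwards, "participants will be asked to provide a rating of perceived exertion for the test".
- **Standing balance:** semi-tandem, full-tandem and single-leg stands (each leg), each tried twice and held as long as possible up to 60 seconds. The end point before the cap is: "The first point in time at which either feet or arms are moved substantially (i.e. loss of balance has occurred) will conclude that attempt". A researcher stands close to give physical support.

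Section 4.4.2 (Screening) admits people scoring no more than 8 of 12 on the SPPB, a limit set to "deliberately target a cohort who demonstrate some degree of compromised strength and balance". Section 4.4.4 repeats the tests at follow-up. If follow-up is remote, the STS-60 and balance tests are done on video with a companion present, and the TUG and the SPPB walk are omitted.

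**The concern.** A risk section should describe the procedures as they will be carried out. Here it reassures about the tests in general, while the procedures ask for a best effort or continue until balance goes, and they provide for stress and falling. The people concerned are memory-clinic outpatients with an MMSE of 20 or more, chosen because their strength and balance are already reduced. For them, plain and accurate wording before consent matters.

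What is at stake is the accuracy of the risk information given before consent. No sample size, endpoint or analysis depends on it.

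**Working it through.** There is no planned figure to reproduce. The check sets the statements side by side.

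**1. Does the risk text reach participants?** Yes, in substance. The end of Section 6 says its content is explained verbally and in the information sheet.

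**2. STS-60.** Section 6 says it will not be challenging. Section 4.4.3 asks for the highest count the person can manage in 60 seconds, collects an exertion rating, and provides for stopping because of stress or fall risk. The statements conflict.

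Section 6 also conflicts with itself. Its opening says participants may find the exercise bouts demanding. Under the intervention section (4.5), each bout begins with one minute of sit-to-stand for as many controlled repetitions as possible. That is essentially the STS-60 task, yet the same paragraph of Section 6 calls the tests unchallenging. A familiar movement is not necessarily an easy one: rising once from a chair is a daily act, whereas rising as often as possible for a minute is not.

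**3. Standing balance.** Section 4.4.3 makes loss of balance one of the two ways an attempt can end, the other being the 60-second cap. It is defined as a substantial movement of feet or arms, which is not the same as a fall. Section 6 does not mention it for the tests.

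**4. Population.** Section 4.4.2 sets the upper SPPB limit in order to enrol people with some degree of compromised strength and balance. That makes it harder to assume these tests are easy for them.

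**5. Extent.**

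- Balance stances: semi-tandem, full-tandem, left leg, right leg = 4.
- Attempts per assessment: 4 x 2 = 8, each capped at 60 seconds.
- STS-60 per assessment: 1.
- Over baseline and follow-up: 8 x 2 = 16 balance attempts and 1 x 2 = 2 STS-60 tests per participant who completes both.

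The documents do not say how many attempts are expected to end in loss of balance.

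**6. Tests not affected.** The TUG and the SPPB walk are fixed courses. Neither runs to a maximum count or to loss of balance, so the conflict does not extend to them.

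**7. Remote follow-up.** Section 4.4.4 keeps the STS-60 and the balance tests but replaces the researcher's physical presence with a companion. A stable item may be placed nearby for the balance measures. Any corrected wording has to cover this case as well as the in-person visit.

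**The case against.** The strongest reply is that this is one over-reassuring clause among adequate safeguards. Much of that stands:

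- Section 4.4.2 has the procedures described, with time for questions, before consent is signed. Section 8 requires hazards to be explained, bars anyone who does not understand, and states the freedom to withdraw.
- Section 4.4.3 has participants told, at the balance tests, to step out of the stance if needed to avoid falling.
- Section 6 says researchers will end a testing session if someone seems unduly stressed.
- The information sheet is not among the documents, so its wording cannot be checked.

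These points limit the harm but do not remove the contradiction. An instruction given at testing is not a disclosure before consent, and readiness to stop a session does not say that balance may be lost.

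A reader might go further and infer that participants are told researchers watch the home exercise, from "The researchers will be at all times vigilant in their observations of participants performing under the prescribed exercise conditions". The documents do not support that. The sentence goes on to speak of ending a testing session. The next paragraph of Section 6 treats home exercise separately, discloses the fall risk and requires another person to be present. Section 4.4.2 describes home exercise as unsupervised.

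**Conclusion.** The point holds as an inconsistency in the risk disclosure. Section 6 is wrong, on the protocol's own account, about the STS-60 and the standing balance tests, and it omits loss of balance from the risks of testing. The extent is one STS-60 and 8 balance attempts per assessment. Nothing statistical changes. It is more than clerical because the content is meant to reach people before they consent.

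A reader might infer that consent would be invalid, or that participants would be left unsafe in the tests. Neither follows. Consent rests on a fuller explanation than this one clause, no safeguard is shown to be missing at the in-person visits, and remote testing requires a companion.

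The conclusion assumes that the closing statement of Section 6 is carried out, so that this content does reach participants. Whether the information sheet repeats the clause is unknown.

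**What to change.** Reconcile Section 6 with Sections 4.4.3 and 4.4.4:

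- Remove the clause saying the tests will not be found challenging.
- Say that the STS-60 asks for as many repetitions as the person can do in a minute, and that the standing balance tests continue until balance is lost or 60 seconds pass.
- Say that participants may find these tests demanding and that loss of balance may occur during them.
- Describe the support as the protocol already provides it: a researcher close by at in-person visits, a companion present at remote follow-up.

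Check the information sheet and make the same change if it carries the same wording.

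The cost is a wording amendment with ethics notification, and possibly a few people declining. Design, tests, sample size, endpoints and analysis stay as they are.
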